Oral glucose tolerance test: Some subjects may experience mild hypoglycemia during the last hour of the OGTT. If a subject complains of dizziness, shakiness, sweating, fast heartbeat or inability to concentrate, a small blood sample will be drawn for testing on the glucometer. If the blood glucose concentration is above 55 mg/dl, a second sample will be tested 10 minutes later. If the blood glucose concentration is still above 55 mg/dl, the OGTT will proceed unless the subject states that they wish to be provided a snack & lunch immediately. If the first blood glucose concentration is below 55 mg/dl, a second blood sample will be drawn and tested immediately. If blood glucose concentration is still below 55 mg/dl, 25 grams of glucose tablets will be provided, followed by snack and lunch. The blood glucose will be rechecked 15 minutes after the glucose tablets/snack/lunch are provided to ensure it has returned to normal range.

The effects of orange juice compared with sugar-sweetened beverage on risk factors and metabolic processes associated with the development of cardiovascular disease and type 2 diabetes

Radiological (DEXA): Subjects will be exposed to a very small amount of x-ray radiation (0.04 mrad) during DEXA procedure. There are no known risks associated with radiation exposure levels this low. There may be some side effects with repeated exposure to radiation, including an increased risk of cancer. However, exposure to doses several thousand times greater than that obtained from this study would be required before an increased risk of cancer could be detected. Thus, the radiation exposure derived from this procedure represents a negligible health risk.

Magnetic resonance imaging (MRI): There is a small risk of that subject will experience anxiety or feelings of claustrophobia during the MRI scan. The radiology technician is in constant communication with the subject and will end the test if subject experiences undue anxiety or claustrophobia. Subjects with pre-existing claustrophobia or metal implants that preclude MRI of the abdominal region will not be enrolled. The MRI scanner makes a loud banging noise that some subjects may find disturbing. Subjects are provided with ear plugs to protect again the loud banging noise. Because the risks to a fetus from MRI are unknown, pregnant participants will not be allowed to participate. Urine pregnancy tests will be conducted before each MRI.

13) Potential Benefits to Subjects

There are no direct benefits to the subjects for participating in the research.

14) Multi-Site Research: N/A

15) Community-Based Participatory Research: N/A

16) Sharing of Results with Subjects

The results that the will be shared with the subjects include the anthropometric results (body weight, waist and hip measurement) and the body composition results generated by DEXA. Upon completion of their participation in the study, subjects will be provided with copies of their clinical chemistry, lipid and blood reports, which were generated on the blood samples collected during screening and during the final week of study. Other study results will not be shared with subjects. In general they will not be available until the end of the 5-year study.

17) Prior Approvals

NIH, the funding agency, will be sent a copy of the IRB-approved Protocol and Consent form for this study, when it is available.

[name] will obtain approval to conduct this research from the Touro University, California Committee on Human Research.

The Human Radiation Use Research Application (Form 35) has approved conduct of the DEXA procedures.

The effects of orange juice compared with sugar-sweetened beverage on risk factors and metabolic processes associated with the development of cardiovascular disease and type 2 diabetes

The UC Davis BUA, #R2217B, for the laboratories of Drs. [name] and [name] was approved on 2/25/19 and is good through 2/28/22.

18) Provisions to Protect the Privacy Interests of Subjects

Following the 30-minute screening survey, most of the interactions with the potential and enrolled subjects that involve providing personal information are handled by the Study Coordinators, research and medical team. We anticipate that our experienced study coordinators and medical team will be able to make the subjects feel at ease with the research situation with honest, open answers about any concerns that the subjects may have. The only information we are unable to share with the subjects will be concerning the metabolic effects we anticipate that we will observe in subjects consuming sucrose. They will be able to share that the amount of sugar in the sugar-sweetened beverages represents an amount that is consumed daily by at least 13% of the US.

As required by NIH, this study will be issued the Certificate of Confidentiality. We will ensure that all research personnel and collaborators listed understand the responsibilities for protecting the confidentiality of the participants' information and will comply with the prohibitions on disclosure. No other collaborator receiving specimens or data will receive identifiable information linking to the participants. Sources of information accessed by the research team include the data collected by the team, including test and scan results, and data generated from subject participation. Subject EMR records will be accessed only for the purpose to assigning them to the study for procedure scheduling and billing purposes. All files pertaining to personal and medical information will be safeguarded using locked filing cases and cabinets, locked offices, password-protected computers and encrypted software.

19) Compensation for Research-Related Injury

We will provide this information to the subjects concerning research-related injury:

Subjects will be informed that it is important that they promptly tell the Researchers if they believe that they have been injured because of taking part in this study. If subjects are injured as a result of being in this study, the University of California will provide necessary medical treatment. The costs of the treatment may be covered by University or by the Principal Investigator's Research Grant. The University does not normally provide any other form of compensation for injury. The subject does not lose any legal rights by signing the consent form.

20) Economic Burden to Subjects

There is no cost to the subject for participating in the study, or for the provision of food and beverage. There will likely be costs for the subjects for transportation to Ragle HNRC twice weekly for meal/beverage pickup/drop-off (approximately 12 times total). Subjects will be offered transportation from Davis to UCDMC and Touro University by study staff in university vehicles. In the case of staff shortages, subjects will be offered transportation from Davis to

The effects of orange juice compared with sugar-sweetened beverage on risk factors and metabolic processes associated with the development of cardiovascular disease and type 2 diabetes

UCDMC and Touro University via rideshare service, such as Uber or Lyft, that the study will pay for or reimburse. Subjects may prefer to drive themselves due to COVID risk. These subjects will be compensated at the UC mileage reimbursement rate for 44 miles to and from UCDMC and for 100 miles to and from TMRC. Additionally, subjects will be compensated \$970 upon completion of the study. This amount may be greater if scheduling adjustments result in a subject remaining on the standardized diet for longer than 47 days. Beyond 47 days, subjects will receive \$10/day for each additional day that they consume the study diet and an additional \$15 for any extra meal pick-up visits. Subjects who do not complete the study will receive prorated compensation as shown in Table 2. Payment forms for each subject will be processed when participation in the study has ended.

If the research involves drugs or device, describe your plans to store, handle, and

21) Drugs or Devices: N/A

administer those drugs or devices so that they will be used only on subjects and be used only by authorized investigators.
 I confirm that all investigational drugs will be received by the Investigational Drug Service (IDS). The IDS will store, handle, and administer those drugs so that they will be used only on subjects and be used only by authorized investigators.
 I confirm that all investigational devices will be labelled in accordance with FDA regulations and stored and dispensed in such a manner that they will be used only on

22) ClinicalTrials.gov Registration

FDAAA 801 establishes penalties for Responsible Parties who fail to comply with Clinical Trials.gov registration or results submission requirements. Penalties include civil monetary penalties and, for federally funded studies, the withholding of grant funds.

For additional information on registration and results submissions requirements click here.

If registration is necessary the following are required:

subjects and be used only by authorized investigators.

- Registration and, in some instances, submission of results at Clinicaltrials.gov
- Specific clinicaltrials.gov language in the consent form for this research. The language can be found in HRP 502 Template Consent under the heading "What happens to the information collected for the research?"

The effects of orange juice compared with sugar-sweetened beverage on risk factors and metabolic processes associated with the development of cardiovascular disease and type 2 diabetes

Complete each section below. If you finish a section indicating the research must be registered on Clinicaltrials.gov is required you do not have to complete the remaining sections.

Section 1: NIH Funded Studies

If yes to BOTH, the study must be registered on Clinicaltrials.gov.

Yes	
\boxtimes	This study is funded by the NIH . (If this study is not funded by NIH, go to Section 2.)
\boxtimes	One or more human subjects will be prospectively assigned to one or more interventions
	(which may include placebo or other control) to evaluate the effects of those
	interventions on health-related biomedical or behavioral outcomes.

Section 2: Studies subject to FDA jurisdiction

If yes to ANY the study must be registered on Clinicaltrials.gov.

Yes	
	This is a prospective clinical study of health outcomes in human subjects that compares an intervention with an FDA-regulated device against a control. This is not a small clinical trial to determine the feasibility of a device, or a clinical trial to test prototype devices where the primary outcome measure relates to feasibility and not to health outcomes.
	This is a pediatric postmarket surveillance of a device as required under section 522 of the Federal Food, Drug, and Cosmetic Act.
	This is a controlled clinical investigation, other than a phase I clinical investigation, of a drug subject to section 505 of the Federal Food, Drug, and Cosmetic Act or to section 351 of the Public Health Service Act.

To view a flowchart describing applicable clinical trials subject to FDA jurisdiction click here.

Section 3: Publishing the results

If yes to BOTH the study must be registered on Clinicaltrials.gov.

Yes	
	This study prospectively assigns people or a group of people to an intervention, with or
	without concurrent comparison or control groups, to study the cause-and-effect
	relationship between a health-related intervention and a health outcome.
	The PI has access to and control over all the data from the clinical trial and has the right
	to publish the results of the trial and plans to publish the results in a journal that follows
	the ICMJE recommendations.

This requirement includes studies of behavioral interventions.

Section 4: Registration on Clinicaltrials.gov is not required

Yes			

	The effects of orange juice compared with sugar-sweetened beverage on risk factors and metabolic processes associated with the development of cardiovascular disease and type 2				
(diabet	es			
		I have read sections 1-3 above and registration on clinicaltrials gov is not required for this research.			

23) Criteria for 10 Year Approval

If yes to all items below this research may qualify for a 10-year approval period.

Yes	
	This research involves no more than minimal risk.
	This research does not receive any federal or state government funding or funding
	from a private funder who requires annual review per contract.
	This research is not subject to FDA jurisdiction.
\boxtimes	This research does not include prisoners as participants.
\boxtimes	This research is not subject to SCRO oversight.
	This research is not subject to oversight by the Research Advisory Panel of
	California (RAP of C).
	This research does not involve identifiable information held by the State of
	California Department or Agency
	No personnel involved in the design, conduct, or reporting of this research have a
	new unreported related financial interest (RFI) in this study.

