Beverage	Kcal	Protein (g)	Fat (g)	Available carbohydrate (g)	Total sugar (g)	Glucose (g)	Fructose (g)	Fiber (g)
Orange Juice	100	1.5	0.3	22.7	19.1	9.1	10.0	0.4
Soda (HFCS-sweetened)	100	0.0	0.0	25.0	23.4	10.5	12.9	0.0
Soda (sucrose-sweetened)	100	0.0	0.0	25.0	25.0	12.5	12.5	0.0

The direct experimental data does not resolve the discrepancy in the epidemiological results. A meta-analysis of 19 randomized controlled trials through 2012 investigating the effects of various fruit juices, concentrated fruit juices and fruit juice powders from elderberry, bilberry, grapefruit, blueberry, cranberry, pomegranate and several types of grape, suggested that fruit juice had a borderline significant effect to reduce diastolic blood pressure, and did not affect total or LDL-C ³⁸. The unaffected lipid levels could be viewed as a positive finding since the majority of the trials utilized control groups that received water intervention or no intervention. However, the dose of provided fruit juice ranged from 40-270 kcal/d, with an approximate mean of 165 kcal/d ³⁸. Possibly the amount of fruit juice consumed in the majority of the 19 studies ³⁸ was too low to induce unfavorable effects in only 2-12 weeks. The low dose group from our recent study, who exhibited increased levels of LDL-C and apoB in 2 weeks, consumed 234 kcal/d as HFCS. A more recent systematic review of the evidence concerning the metabolic impact of 100% fruit juice consumption concluded evidence-based recommendations were not possible⁵.

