Anyone coming onto campus (students, employees or visitors) is required to follow the university COVID-19 safety guidelines that are posted on the campus website: https://campusready.ucdavis.edu/, which may include filling out the UC Davis Daily Symptom Survey during each visit and completing COVID-19 testing. Additionally, participants will be required to wear a mask during all study interactions, have their temperature monitored and maintain a 6-foot distance when possible (e.g., except Registered Nurses performing blood draws). For transport by study staff in UCD vehicles to study procedure sites, participants will be provided and required to wear a KN95 or N95 mask, face shield and to sit 6 feet away from the driver and any other passenger.

General study design: The study is designed as a parallel, 6-week study with a 2-week baseline period during which all subjects consume the provided low-sugar baseline diet and a 4-week intervention period during which the experimental beverages are consumed along with a low-sugar diet.

Baseline (Week 1-2): All subjects will consume a provided, standardized, low sugar, energy-balanced diet for approximately 9-13 days. All experimental procedures are conducted. **Intervention (Week 3-6):** Subjects will be stratified by gender and normal weight/overweight status and randomized to one of the two groups listed below:

- **1.** Sugar-sweetened beverages (SSB): 25% of estimated Ereq/day as sucrose in water (11% weight/w/w), flavored with unsweetened Kool-Aid and divided into 3 servings/day.
- **2. Orange Juice (OJ)**: 25% of estimated Ereq/day as the carbohydrate in OJ divided into 3 servings/day.

Subjects will consume three provided beverages/day along with provided, standardized, energy-balanced meals and snacks for approximately 28-33 days. All experimental procedures are repeated.

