Food is served/provided as 3 meals and a snack, with 23% of the energy provided as breakfast, 32.5% as lunch, 37% as dinner and 7.5% as snack. Meals and snacks mainly consist of a heterogeneous mix of ingredients (i.e. stir-fry or casserole rather than separate servings of meat, grain and vegetable) formulated to the standardized specifications. This ensures that a subject who does not eat an entire meal is still consuming the required macronutrient distribution. The intervention meals contain 25% more fiber than the baseline meals in order that the fiber content of both the overall baseline and intervention (which includes the beverages) diets is 12.5 g/1000 kcals. This is mainly achieved by a greater proportion of unrefined grains (e.g. whole wheat pasta) in the intervention meals. The overall fat content of the baseline and intervention diets is <10% E_{req} saturated fat, and $\sim12\%$ and $\sim13\%$ E_{req} polyunsaturated and mono-unsaturated fat, respectively.

Beverages: We will utilize unfortified 100% orange juice that is pasteurized, ready-to-serve, and is not reconstituted from concentrate. We will utilize a top-selling brand and type that is widely available. The SSB will be made with sucrose from beet sugar at a weight/weight concentration to ensure that subjects with identical energy requirements will receive the identical volume of beverage, whether it be orange juice or SSB. Samples of each beverage batch are retained and frozen for future quality control and nutrient/bioactive analyses. Subjects are provided with 25% of daily E_{req} as the total carbohydrate in their assigned beverage (carbohydrate in orange juice is approximately 90% sugar and 10% oligosaccharides), divided into 3 daily servings to be consumed with meals (25% at breakfast, 35% at lunch, 40% at dinner). Subjects are required to consume all the beverage provided. The beverages will contain a biomarker (riboflavin) that will be assayed fluorometrically in urine collected 2 times/week during meal pick-up appointments (See Compliance monitoring section below).

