To identify subjects who consume or consumed non-study foods that contained HFCS or cane sugar or consume alcoholic beverages during the study period, we will measure biomarkers for added sugar and alcohol intake. We will measure the delta ¹³C value of blood drops collected at baseline and at the end of 4 weeks of intervention. The Delta ¹³C content in the blood drop will be measured at the UCD Stable Isotope Facility. Delta ¹³C is a novel validated biomarker of added sugar intake because most plants have a low natural abundance of delta ¹³C, while that of corn and sugar cane is conspicuously higher ^{110, 111}. The foods with the highest amounts of delta ¹³C are pure corn products, and beverages, hard candies and desserts sweetened with HFCS or cane sugar. Sugar from sugar beets has a low natural abundance of delta ¹³C, therefore beet sugar will be used to sweeten the sucrose-sweetened beverages provided as part of the intervention. Delta ¹³C in blood is an indicator of added HFCS and sugar cane sucrose consumption over the prior 2 weeks ³. Because all the meals and snacks provided during the 6-week study have a very low HFCS and sugar cane content, and all subjects are consuming the same foods, all compliant subjects will exhibit low and comparable levels of blood delta ¹³C at both the end of the 2nd week and 6th week of study. Data from subjects with delta ¹³C blood values that are more than 2 standard deviations above the mean for all subjects will not be included in the statistical analyses.

To identify subjects who routinely consume alcohol we will assay urinary ethyl glucuronide (immunoassay, Thermo Scientific, Fremont, CA) in the urine samples collected at each meal pick-up visit. Detection of ethyl glucuronide in urine indicates recent alcohol consumption ¹¹² and is considered to be a specific, highly sensitive, and reliable marker of recent alcohol intake within the previous 5 days ⁴. Urinary ethyl glucuronide concentrations above the 500 ng/ml will be considered positive for alcohol intake. Urine will be monitored for alcohol intake upon collection, and subjects with positive values will be considered for dismissal. The subjects will be informed that they are being monitored for compliance to the requirement that they not consume non-study food, but will not be provided specifics as to the method.

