			7:00	Transport to TMRC, Consumption of acetate tracer dose	
			8:00	Check-in, vitals, anthropometrics, catheter insertion	
			8:45	Start blood collection every 30 or 60 minutes	
2	TMRC Visit #1	TMRC	9:00 - 12:00	Oral glucose tolerance test	\$150
			12:00	Lunch, Consumption of acetate tracer dose	
			13:00 - 15:00	Study questionnaires, DEXA scan	
			13:00 - 15:00 16:00	Study questionnaires, DEXA scan Dinner, Consumption of acetate tracer dose	
Interv	vention ~ 4 weeks	Energy-bala	16:00 20:00 anced intervention of	Dinner, Consumption of acetate tracer dose Final blood draw, remove catheter, check-out diet: Orange juice or SSB (25%Ereq), carbohydrate (ma Ereq), fat (35%Ereq), protein (15%Ereq)	inly starch
Interv	vention ~ 4 weeks	Energy-bala Home/Ragle HNRC	16:00 20:00 anced intervention of	Dinner, Consumption of acetate tracer dose Final blood draw, remove catheter, check-out diet: Orange juice or SSB (25%Ereq), carbohydrate (ma	inly starch \$140
		Home/Ragle	16:00 20:00 anced intervention of 25%	Dinner, Consumption of acetate tracer dose Final blood draw, remove catheter, check-out diet: Orange juice or SSB (25%Ereq), carbohydrate (ma Ereq), fat (35%Ereq), protein (15%Ereq) Consumption of provided intervention study meals & beverages Pick-up/dropoff for study meals/beverages; urine	
3-6	Diet	Home/Ragle HNRC	16:00 20:00 anced intervention of 25% TBD by subject	Dinner, Consumption of acetate tracer dose Final blood draw, remove catheter, check-out diet: Orange juice or SSB (25%Ereq), carbohydrate (ma Ereq), fat (35%Ereq), protein (15%Ereq) Consumption of provided intervention study meals & beverages Pick-up/dropoff for study meals/beverages; urine collection: 2 times/week	\$140
3-6	Diet 24-h UC #2	Home/Ragle HNRC Home	16:00 20:00 anced intervention of 25% TBD by subject TBD by subject	Dinner, Consumption of acetate tracer dose Final blood draw, remove catheter, check-out diet: Orange juice or SSB (25%Ereq), carbohydrate (ma Ereq), fat (35%Ereq), protein (15%Ereq) Consumption of provided intervention study meals & beverages Pick-up/dropoff for study meals/beverages; urine collection: 2 times/week 24 hour urine collection	\$140 \$40

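### Do 25% more meal fiber and 12.5 g/1000 kcal overall contradict each other in a way that requires a change to the plan?

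*Combined protocol and SAP*

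**What the plan says.** In the protocol's section 7 (Procedures Involved), the text under Diets & weight monitoring gives one percentage and one result for the intervention diet: "The intervention meals contain 25% more fiber than the baseline meals in order that the fiber content of both the overall baseline and intervention", with the beverages counted on the intervention side, "diets is 12.5 g/1000 kcals". It does not say whether the percentage refers to grams or to grams per kcal. It also does not say whether the snack is included, although the paragraph opens with "Food is served/provided as 3 meals and a snack".

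Under General study design, the sucrose arm (SSB) receives "25% of estimated Ereq/day as sucrose in water" and the juice arm (OJ) receives "25% of estimated Ereq/day as the carbohydrate in OJ divided into 3 servings/day". The diet section has this carbohydrate replace an equal share of complex carbohydrate. Table 1 in section 3 (Background) lists sucrose-sweetened soda at 0.0 g fiber per 100 kcal, and orange juice at 0.4 g fiber and 22.7 g available carbohydrate. Under Compliance monitoring, the argument for the blood carbon-13 marker remarks that "all subjects are consuming the same foods".

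**The concern.** The sentence on fiber is a matching specification: diets are meant to differ from baseline only in the carbohydrate substitution. A quarter of the SSB arm's energy comes from a fiber-free drink, so the remaining food must carry all the fiber. A 25% rise does not make up for a 25% loss of energy from food. If the juice contributes fiber and the meals are common, the arms also cannot share one overall figure.

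The primary endpoints include blood lipids and lipoproteins. A reader could therefore worry that fiber fell from baseline in the SSB arm, or differed between arms, and that this would be mixed into the beverage effect. At the least, a report repeating 12.5 for both arms might be inaccurate.

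**Working it through.** **Inputs.** Overall target 12.5 g/1000 kcal and rise of 25% (Diets & weight monitoring). Beverage carbohydrate 25% of energy requirement (General study design). SSB fiber 0. Juice fiber 0.4 g and carbohydrate 22.7 g per 100 kcal (Table 1). Table 1's sucrose row, 25.0 g per 100 kcal, implies 4 kcal/g. Assumption: the baseline diet is food only, at 12.5.

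**SSB arm, per 1000 kcal** (food 750 kcal, drink 250 kcal with no fiber):

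- Rise in density: meals 12.5 × 1.25 = 15.625 g/1000 kcal; overall 15.625 × 0.75 = 11.72. Shortfall 12.5 − 11.72 = 0.78, and 0.78/12.5 = 6%.
- Rise in grams: 12.5 × 1.25 = 15.6.
- Rise needed for 12.5: 12.5/0.75 = 16.67, and 16.67/12.5 = 1.333, or +33.3%. On that basis baseline density is 12.5/16.67 = 0.75 of intervention density, which is 25% lower.
- Rounding does not explain it: 12.55 × 1.255 × 0.75 = 11.81, still below 12.45.
- Exempting the snack (7.5% of the 750 kcal, or 56.25 kcal, left at 12.5): 0.69375 × 15.625 + 0.05625 × 12.5 = 11.54.

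So the stated 12.5 is not reproduced for this arm from the literal 25%.

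**OJ arm, using Table 1 and common meals.** Carbohydrate energy is 22.7 × 4 = 90.8 kcal per 100 kcal of juice. Supplying 250 kcal as carbohydrate takes 250/0.908 = 275.3 kcal of juice, containing 275.3 × 0.4/100 = 1.10 g fiber. Food is either kept at 750 kcal (total 1025.3) or cut to 724.7 kcal (total 1000).

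| Rise in meal density | Food 750 kcal | Food 724.7 kcal | SSB |
|---|---|---|---|
| +25% | (11.72 + 1.10)/1.0253 = 12.50 | 15.625 × 0.7247 + 1.10 = 12.42 | 11.72 |
| +33.3% | (12.50 + 1.10)/1.0253 = 13.27 | 16.67 × 0.7247 + 1.10 = 13.18 | 12.50 |

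The gap between arms is about 0.7 to 0.8 g/1000 kcal in either row.

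**How far the juice result depends on Table 1.** At +33.3% SSB is at 12.5. OJ is also at 12.5 if the juice supplies 12.5 × 1.0253 − 12.50 = 0.316 g in 275.3 kcal (about 0.11 g per 100 kcal) with food at 750 kcal. With food cut, the amount is 12.5 − 12.08 = 0.42 g (about 0.15 g per 100 kcal). The documents give no fiber value for the juice actually used, so they do not exclude this.

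**Daily size.** At an assumed 2,000 to 3,000 kcal/day, 0.78 g/1000 kcal is 1.6 to 2.3 g/day for SSB.

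**Where the figure is used.** Section 6 (Study Endpoints) has no fiber outcome. The data analysis plan in section 8 models change from baseline on beverage, gender and protocol version, adjusted for BMI and the baseline outcome; its example covariates do not include fiber. The sample size paragraph rests on effect sizes of 0.89, 0.84 and 1.02 for LDL-C, apoB and uric acid. None of these takes 25% or 12.5 g/1000 kcal as an input.

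**The case for a change.** The strongest case for acting is that the SSB mismatch needs no outside data. A fiber-free drink at 25% of energy is enough, and rounding, a grams basis and a snack exemption all leave the SSB figure away from 12.5. Even arm-specific meals would not rescue the sentence on Table 1's juice values, because one percentage would then have to describe a rise of 33.3% in one arm and a smaller rise in the other. The correction would cost a sentence or two. That part of the arithmetic stands.

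The wider claim, that no reading can give 12.5 in both arms, does not stand. It relies on a background table that is not tied to the study juice. It also relies on common meals, which are inferred from the single meal description and from a remark made to justify a sugar biomarker. The schedule heading "Orange juice or SSB (25%Ereq" is reasonably read as shorthand for the carbohydrate basis stated elsewhere, so it does not establish a second dose definition.

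On consequences, the fiber gap with common meals comes from the juice itself and is part of what randomization compares. A 6% fall from baseline in the SSB arm could in principle touch the tests of change from zero. However, the documents give nothing that links 0.78 g/1000 kcal to any outcome, and no recipes to show that the fall occurred.

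**Conclusion.** The literal 25% and 12.5 g/1000 kcal do not agree for the SSB arm: 11.7 if the rise is in density (6% low), 15.6 if in grams, and +33.3% would be needed. This rests on a fiber-free drink, 75% of energy from food, and a baseline of 12.5. For the OJ arm the figures are about 12.4 to 12.5 at +25%, or 13.2 to 13.3 at +33.3%, but only with Table 1's juice and common meals. The documents do not show which number is the slip, or that any meal was made wrongly.

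This is a clerical inconsistency in a diet description. Correcting it would alter no endpoint, covariate, power figure or decision rule, and would leave the randomized comparison and its interpretation as they are. Those reporting the diets can take the fiber density of each arm from the recipes and from the intake calculated from returned food. No change to the plan follows.
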